8.2.7. Chest X-Ray and Tuberculosis Testing

An anterior-posterior view chest x-ray will be obtained, unless the x-ray or results from a chest x-ray obtained within 6 months before the study are available. The chest x-ray or results will be reviewed by the investigator or designee to exclude participants with active TB infection prior to enrollment.

Tuberculosis testing will be conducted based on clinical assessment of TB risk (symptoms, signs, and known or suspected TB exposure), and as required by local regulations and/or local standard of care. Participants with a positive TB test and/or other evidence of active TB should be discontinued (Section 7.1.1).

Tuberculosis testing – QuantiFERON® TB Gold will be the preferred testing option for TB. The QuantiFERON® TB Gold test may be performed locally or centrally. If the QuantiFERON®-TB Gold test is indeterminate (not negative), 1 retest is allowed. If the retest for the QuantiFERON®-TB Gold test is indeterminate (not negative), the participant is excluded from enrollment in the study.

In countries where the QuantiFERON®-TB Gold test is not available or due to investigator's judgement (e.g., need to reduce the volume of blood collected), the T-Spot or PPD test may be used. In the case of selecting the PPD test, the participant must return within 48 to 72 hours to read the skin test.

A positive PPD skin test response for this study is defined as ≥ 5 -mm induration between 48 and 72 hours after PPD application, regardless of BCG vaccination history.

Participants with a PPD skin test ≥ 5 mm induration or a positive QuantiFERON®-TB Gold or T-Spot test but no evidence of active TB, and participants who have a documented history of a positive TB test but no documented history of completion of a full, appropriate latent TB treatment course, who are assessed as having latent TB infection may be re-screened 1 time and may be enrolled without repeating a QuantiFERON®-TB Gold, T-Spot or PPD test if the following conditions are met:

- after receiving at least 4 weeks of appropriate latent TB infection therapy with no evidence of hepatotoxicity (ALT/AST must remain $\leq 2 \times$ ULN) upon retesting of serum ALT/AST prior to enrolment,
- commitment by the participant and the caregiver for the participant to complete a full course of standard prophylaxis for TB, and
- meet all other inclusion/exclusion criteria for participation.

Such participants must complete appropriate latent TB infection therapy to remain eligible for continued study participation. If rescreening occurs within 6 months of the screening chest x-ray, a repeat of chest x-ray for considering enrollment is not required.

If a participant with a positive QuantiFERON®-TB Gold or T-Spot or PPD is fully assessed by the investigator and the investigator determines that the participant has no risk factors for and no symptoms or signs of *Mycobacterium tuberculosis* infection, the investigator may contact the Sponsor's medical monitor to discuss the possibility of a false-positive test result.

Participants with positive TB test results on file: Participants with a documented prior history of a positive TB test and participants who have a documented history of completion of an appropriate TB treatment regimen for latent or active TB should not have a TB test performed at Visit 1. Such participants with no history of re-exposure to TB since their treatment was completed and no evidence of active TB are eligible to participate in the study. Participants who have had household contact with a person with active TB are excluded unless an appropriate and documented course of prophylaxis for TB was completed.

Participants are to be monitored on a regular basis for any symptoms or signs of active TB and for any new risk factors for TB infection, with full medical evaluation including TB testing when medically indicated. Participants that exhibit symptoms of active TB should be referred to a specialist in the care of participants with TB.

Any clinically significant findings from TB testing that result in a diagnosis and that occur after the participant signs the ICF should be reported to the Sponsor or its designee as an AE via eCRF.

8.2.8. Safety Monitoring

The Sponsor will periodically review evolving aggregate safety data within the study by appropriate methods.

8.2.8.1. Hepatic Safety Monitoring

Close hepatic monitoring

Laboratory tests (Appendix 10.5), including ALT, AST, alkaline phosphatase (ALP), total bilirubin (TBL), direct bilirubin, gamma-glutamyltransferase (GGT), and creatine kinase (CK), should be repeated within 48 to 72 hours to confirm the abnormality and to determine if it is increasing or decreasing, if one or more of these conditions occur:

If a participant with baseline results of ...	develops the following elevations:
ALT or AST $<1.5 \times$ ULN	ALT or AST $\geq 3 \times$ ULN
ALP $<1.5 \times$ ULN	ALP $\geq 2 \times$ ULN
TBL $<1.5 \times$ ULN	TBL $\geq 2 \times$ ULN (except for participants with Gilbert's syndrome)
ALT or AST $\geq 1.5 \times$ ULN	ALT or AST $\geq 2 \times$ baseline
ALP $\geq 1.5 \times$ ULN	ALP $\geq 2 \times$ baseline
TBL $\geq 1.5 \times$ ULN	TBL $\geq 2 \times$ baseline (except for participants with Gilbert's syndrome)

If the abnormality persists or worsens, clinical and laboratory monitoring, and evaluation for possible causes of abnormal liver tests should be initiated by the investigator in consultation with the Lilly-designated medical monitor. At a minimum, this evaluation should include physical examination and a thorough medical history, including symptoms, recent illnesses (e.g., heart failure, systemic infection, hypotension, or seizures), recent travel, history of concomitant medications (including over-the-counter), herbal and dietary supplements, and a history of alcohol drinking and other substance abuse.

Initially, monitoring of symptoms and hepatic biochemical tests should be done at a frequency of 1 to 3 times weekly, based on the participant's clinical condition and hepatic biochemical tests. Subsequently, the frequency of monitoring may be decreased to once every 1 to 2 weeks, if the participant's clinical condition and laboratory results stabilize. Monitoring of ALT, AST, ALP, and TBL should continue until levels normalize or return to approximate baseline levels.

Comprehensive hepatic evaluation

A comprehensive evaluation should be performed to search for possible causes of liver injury if one or more of these conditions occur:

If a participant with baseline results of...	develops the following elevations:
ALT or AST $<1.5 \times$ ULN	ALT or AST $\geq 3 \times$ ULN with hepatic signs/symptoms*, or ALT or AST $\geq 5 \times$ ULN
ALP $<1.5 \times$ ULN	ALP $\geq 3 \times$ ULN
TBL $<1.5 \times$ ULN	TBL $\geq 2 \times$ ULN (except for participants with Gilbert's syndrome)
ALT or AST $\geq 1.5 \times$ ULN	ALT or AST $\geq 2 \times$ baseline with hepatic signs/symptoms,* or ALT or AST $\geq 3 \times$ baseline
ALP $\geq 1.5 \times$ ULN	ALP $\geq 2 \times$ baseline
TBL $\geq 1.5 \times$ ULN	TBL $\geq 1.5 \times$ baseline (except for participants with Gilbert's syndrome)

* Hepatic signs/symptoms are severe fatigue, nausea, vomiting, right upper quadrant abdominal pain, fever, rash, and/or eosinophilia $>5\%$.

At a minimum, this evaluation should include physical examination and a thorough medical history, as outlined above, as well as tests for prothrombin time - international normalized ratio (PT-INR); tests for viral hepatitis A, B, C, or E; tests for autoimmune hepatitis; and an abdominal imaging study (e.g., ultrasound or CT scan).

Based on the participant's history and initial results, further testing should be considered in consultation with the Lilly-designated medical monitor, including tests for hepatitis D virus (HDV), cytomegalovirus (CMV), Epstein-Barr virus (EBV), acetaminophen levels, acetaminophen protein adducts, urine toxicology screen, Wilson's disease, blood alcohol levels, urinary ethyl glucuronide, and serum phosphatidylethanol. Based on the circumstances and the investigator's assessment of the participant's clinical condition, the investigator should consider referring the participant for a hepatologist or gastroenterologist consultation, magnetic resonance cholangiopancreatography (MRCP), endoscopic retrograde cholangiopancreatography (ERCP), cardiac echocardiogram, or a liver biopsy.

8.2.8.1.1. Additional Hepatic Data Collection in Participants Who Have Abnormal Liver Tests During the Study

Additional hepatic safety data collection in hepatic safety eCRFs should be performed in study participants who meet 1 or more of the following 5 conditions:

- Elevation of serum ALT to $\geq 5 \times$ ULN on 2 or more consecutive blood tests (if baseline ALT $<1.5 \times$ ULN):
 - In participants with baseline ALT $\geq 1.5 \times$ ULN, the threshold is ALT $\geq 3 \times$ baseline on 2 or more consecutive tests;
- Elevated TBL to $\geq 2 \times$ ULN (if baseline TBL $<1.5 \times$ ULN) (except for cases of known Gilbert's syndrome):
 - In participants with baseline TBL $\geq 1.5 \times$ ULN, the threshold should be TBL $\geq 2 \times$ baseline;
- Elevation of serum ALP to $\geq 2 \times$ ULN on 2 or more consecutive blood tests (if baseline ALP $<1.5 \times$ ULN):

- In participants with baseline ALP $\geq 1.5 \times$ ULN, the threshold is ALP $\geq 2 \times$ baseline on 2 or more consecutive blood tests;
- Hepatic event considered to be an SAE;
- Discontinuation of study intervention due to a hepatic event.

Note: the interval between the 2 consecutive blood tests should be at least 2 days.

8.2.8.2. Hepatitis C Testing and Monitoring

Initial testing for HCV infection includes testing for antibodies to HCV:

- If anti-HCV is positive, a serum test for circulating HCV RNA is required.
- If HCV RNA test is negative, the participant is not excluded.
- If HCV RNA test is positive, the participant is excluded.

Participants who have had HCV infection and been successfully treated, defined as a sustained virologic response (HCV RNA by PCR-negative for at least 24 weeks following treatment completion) are not excluded on the basis of HCV as long as HCV RNA test is negative at screening.

If HCV RNA is detected during the study, the study intervention will be discontinued (see Section 7.1.1), and the participant should receive appropriate follow-up medical care.

8.2.8.3. Hepatitis B Testing and Monitoring

Initial testing for hepatitis B virus (HBV) infection includes hepatitis B surface antigen (HBsAg) and antibody to hepatitis B core antigen (anti-HBc):

- If HBsAg is positive, the participant is excluded;
- If HBsAg is negative and anti-HBc is negative, the participant is not excluded;
- If HBsAg is negative and anti-HBc is positive, further testing for HBV DNA is required:
 - If the screening HBV DNA is positive, the participant is excluded;
 - If the screening HBV DNA is negative, the participant is not excluded. Repeat testing for HBV DNA is required at least every 3 months during the study (see the SoA [Section 1.3]), with temporary withholding or permanent discontinuation of study intervention if HBV DNA is positive, as described in Section 7.1.1.

Management of enrolled participants with detectable HBV DNA during the study

If HBV DNA is detected during the study, the study intervention will be temporarily withheld or permanently discontinued, and participants should receive appropriate follow-up medical care as described in Section 7.

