5.2. Exclusion Criteria

Participants are excluded from the study if any of the following criteria apply:

- [12] Have previously completed or withdrawn from this study, participated in any other study with ixekizumab, or have participated in any study investigating other IL-17 antagonists.
- [13] Have a history of drug-induced PsO.
- [14] Concurrent or recent use of any biologic agent within the following washout periods: etanercept <28 days; infliximab, adalimumab, or alefacept <60 days; golimumab <90 days; ustekinumab <8 months; rituximab or efalizumab <12 months; or any other biologic agent <5 half-lives prior to baseline (Week 0 Visit 2).
- [15] Cannot avoid excessive sun exposure or use of tanning booths for at least 4 weeks prior to baseline (Week 0; Visit 2) and during the study.
- [16] Have a known allergy or hypersensitivity to any biologic therapy that would pose an unacceptable risk to the patient if participating in this study.
- [17] Have ever received natalizumab or other agents that target alpha-4-integrin.
- [18] Had a live vaccination within 12 weeks prior to baseline (Week 0; Visit 2), or intend to have a live vaccination during the course of the study, or within 12 months of completing treatment in this study, or have participated in a vaccine clinical study within 12 weeks prior to baseline (investigators should review the vaccination status of their patients and follow the local guidelines for adult vaccination with non-live vaccines intended to prevent infectious disease prior to therapy).

Note: Killed/Inactive or subunit vaccines are expected to be safe; however, their efficacy with concomitant ixekizumab treatment is unknown.

- [19] Had a vaccination with Bacillus Calmette-Guérin (BCG) within 12 months prior to baseline (Week 0; Visit 2), or intend to have this vaccination with BCG during the course of the study, or within 12 months of completing treatment in this study.
- [20] Had any major surgery within 8 weeks prior to baseline (Week 0; Visit 2), or will require such during the study that, in the opinion of the investigator in consultation with Lilly or its designee, would pose an unacceptable risk to the patient.
- [21] Have current or a history of lymphoproliferative disease; or signs or symptoms of lymphoproliferative disease; or have active or history of malignant disease.
- [22] Have diagnosis or history of malignant disease within the 5 years prior to baseline (Week 0, Visit 2).

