Note: Participants with only recurrent mild and uncomplicated orolabial herpes, or genital herpes, or both may be discussed with the Sponsor's designated medical monitor and considered for enrollment if other study eligibility criteria are met.

[27] Have active TB (refer to Section 8.2.7 for details on determining full TB exclusion criteria).

[28] Have any other active or recent infection within 4 weeks of baseline (Week 0; Visit 2) that, in the opinion of the investigator, would pose an unacceptable risk to the patient if participating in the study; these patients may be rescreened (1 time) 4 or more weeks after documented resolution of symptoms.

[29] Have a body temperature $\geq 38^{\circ}\text{C}$ (100.5°F) at baseline (Week 0; Visit 2); these patients may be rescreened (1 time) ≥ 4 weeks after documented resolution of elevated temperature.

[30] Have uncontrolled arterial hypertension characterized by a systolic blood pressure (SBP) >160 mm Hg or diastolic blood pressure (DBP) >100 mmHg.

Note: Determined by 2 consecutive elevated readings. If an initial blood pressure (BP) reading exceeds this limit, the BP may be repeated once after the patient has rested sitting for ≥ 10 minutes. If the repeat value is less than the criterion limits, the second value may be accepted.

[31] Are positive for human immunodeficiency virus (HIV) serology (positive for human immunodeficiency virus antibody [HIVAb]).

[32] Have evidence of or test positive for hepatitis B by any of the following criteria:
1) positive for hepatitis B surface antigen (HBsAg+); 2) positive for anti-hepatitis B core antibody (HBcAb+) and negative for anti-hepatitis B surface antibody (HBsAb-); 3) positive for anti-hepatitis B core antibody (HBcAb+) and positive for anti-hepatitis B surface antibody (HBsAb+) with a concentration of HBsAb <200 mIU/mL; or 4) HBcAb+, HBsAb+ (regardless of HBsAb level), and positive for serum hepatitis B virus (HBV) DNA.

Note: Patients who are negative for hepatitis B surface antigen (HBsAg-), HBcAb+, HBsAb+ with a concentration of HBsAb \geq 200 mIU/mL, and negative for serum HBV DNA may participate in the study. Patients who meet these criteria at screening will be identified by the central laboratory and monitored during the study as detailed in Section 8.2.8.1.

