10.2 Appendix 2: Clinical Laboratory Tests

The tests detailed in the table below will be performed by the central laboratory or by the local laboratory as specified in the table.

Protocol-specific requirements for inclusion or exclusion of participants are detailed in Section 5 of the protocol.

Additional tests may be performed at any time during the study as determined necessary by the investigator or required by local regulations.

Pregnancy testing is described in the SoA (Section 1.3) and in the table below.

Investigators must document their review of each laboratory safety report.

Due to blood volume restrictions, some laboratory tests may not be collected. Laboratory samples are recommended to be collected as described in the Sponsor provided weight-based prioritization chart.

Hematology^{a,b}

Hemoglobin
Hematocrit
Erythrocyte count (RBC)
Mean cell volume (MCV)
Mean cell hemoglobin concentration (MCHC)
Leukocytes (WBC)
Platelets

Absolute counts of:

Neutrophils, segmented
Neutrophils, juvenile (bands)
Lymphocytes
Monocytes
Eosinophils
Basophils

Urinalysis^{a,b}

Color
Specific gravity
pH
Protein
Glucose^g
Ketones
Bilirubin
Urobilinogen
Blood
Nitrite
Urine creatinine
Leukocyte esterase
Urinalysis (microscopic):
Sediment, cells, casts

Serum Chemistry^{a,b}

Sodium
Potassium
Bicarbonate
Chloride
Phosphorus
Total bilirubin
Direct bilirubin
Indirect bilirubin
Alkaline phosphatase
Alanine aminotransferase (ALT/SGPT)
Aspartate aminotransferase (AST/SGOT)
Blood urea nitrogen (BUN)
Uric acid
Creatinine
Calcium
Glucose^g
Albumin
Cholesterol (total)
Total protein
CPK
Triglycerides
Gamma-Glutamyl Transferase (GGT)

Other Tests^aHuman immunodeficiency virus antibody (HIV)^{c,d}Hepatitis B Surface antigen (HBsAg)^{c,d}Anti-Hepatitis B Core antibody (HBcAb)^{c,d}Anti-Hepatitis B Surface antibody (HBsAb)^dAnti-Hepatitis C^dHBV DNA^{c,d}Pregnancy Test (serum and urine)^eFollicle stimulating hormone (FSH)^{d,f}Tuberculosis^d

Abbreviations: CPK = creatine phosphokinase; DNA = deoxyribonucleic acid; HBV = hepatitis B virus; RBC = red blood cells; SGOT = serum glutamic oxaloacetic transaminase; SGPT = serum glutamic pyruvic transaminase; WBC = white blood cells.

^a Assayed by Sponsor-designated laboratory.

^b Unscheduled blood chemistry, urinalysis, and hematology panels may be performed at the discretion of the investigator.

^c See exclusion criteria (Section 5.2).

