^d Test required at Visit 1 only to determine eligibility of participant for the study (with the exception of those participants who require further HBV monitoring [Section 8.2.8.3]).

^e Serum pregnancy test (women <60 years of age who are still of childbearing potential) and urine pregnancy test (women of childbearing potential). Participants will undergo urine pregnancy self-testing at home on a monthly basis during periods between scheduled visits until Week 24. During these intervisit periods, the site must call the participant each month to obtain her pregnancy test results. Additional urine pregnancy testing can be performed at the investigator's discretion. Participants determined to be pregnant will be discontinued from treatment and will no longer be administered study intervention (see Section 7.1.1).

^f Women ≥40 and <60 years of age who have had a cessation of menses for ≥12 months will have an FSH test confirming nonchildbearing potential (≥40 mIU/mL). The FSH test will be performed centrally.

^g Non-fasting glucose.

10.3 Appendix 3: Adverse Events and Serious Adverse Events: Definitions and Procedures for Recording, Evaluating, Follow-up, and Reporting

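### Section 8.2.8.3 does not exclude any HBV-DNA-negative, core-antibody-positive participant, but exclusion [32] bars those whose surface antibody is negative or below 200 mIU/mL

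*Protocol*

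**What the plan says.** **Section 8.2.8.3** sets out a decision tree. Its first step is "Initial testing for hepatitis B virus (HBV) infection includes hepatitis B surface antigen (HBsAg) and antibody to hepatitis B core antigen (anti-HBc"). HBsAg-positive candidates are excluded, and candidates negative on both markers are not. Candidates who are HBsAg-negative and anti-HBc-positive go on to HBV DNA testing. If DNA is positive they are excluded; otherwise, "If the screening HBV DNA is negative, the participant is not excluded". That last group then has HBV DNA repeated at least every 3 months. The section never mentions HBsAb and does not refer to exclusion [32].

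**Section 5.2** opens with "Participants are excluded from the study if any of the following criteria apply". Within it, [32] has four alternative hepatitis B criteria:

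- Item 1: HBsAg-positive.
- Item 2: "positive for anti-hepatitis B core antibody (HBcAb+) and negative for anti-hepatitis B surface antibody (HBsAb"-negative).
- Item 3: "positive for anti-hepatitis B core antibody (HBcAb+) and positive for anti-hepatitis B surface antibody (HBsAb+) with a concentration of HBsAb <200 mIU/mL".
- Item 4: both antibodies positive at any HBsAb level, with HBV DNA positive.

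Items 2 and 3 carry no DNA condition. The note to [32] allows participation for HBsAg-negative, core-antibody-positive patients with HBsAb of at least 200 mIU/mL and negative DNA. It says that these patients "will be identified by the central laboratory and monitored during the study as detailed in Section 8.2.8.1".

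**Appendix 2 (Section 10.2)** states: "Protocol-specific requirements for inclusion or exclusion of participants are detailed in Section 5 of the protocol". It lists HBsAb as a Visit 1 eligibility test. Its footnote d limits the listed tests to Visit 1 "with the exception of those participants who require further HBV monitoring [Section 8.2.8.3"].

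**The concern.** Both passages are current protocol text, and each gives a definite answer for the same people. Section 8.2.8.3 is more than silent on HBsAb: every branch ends in an excluded or not-excluded decision, so it reads as a self-contained eligibility rule. The hepatitis C section just before it (8.2.8.2) has the same form and broadly agrees with its own criterion, [33], so a site has reason to treat these trees as operative.

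The cross-references make matters worse. The note to [32] and footnote l of the Schedule of Activities both send the reader to Section 8.2.8.1 for hepatitis B monitoring. That section covers liver-enzyme monitoring and contains no HBV DNA schedule. A reader of [32] is therefore sent to the wrong section, and a reader of 8.2.8.3 is not sent to [32] at all.

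What is at stake is participant safety and eligibility compliance. [32] bars people at risk of HBV reactivation. Enrolling one of them on the strength of 8.2.8.3 would be an eligibility deviation. Section 5 does not permit waivers, and Section 7.2.1 would require the inadvertent-enrolment process. Such a participant would also lie outside the group that the [32] note singles out for central-laboratory identification and monitoring.

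**Working it through.** The protocol gives no figure to reproduce. The check applies both rules to every profile of an HBsAg-negative, anti-HBc-positive candidate.

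Inputs: the four items and note of [32] (Section 5.2), and the decision tree in Section 8.2.8.3.

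Profiles: HBsAb {negative; positive below 200 mIU/mL; positive at 200 mIU/mL or more} × HBV DNA {negative; positive} = 3 × 2 = 6.

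| HBsAb | HBV DNA | Exclusion [32] | Section 8.2.8.3 | Agree? |
|---|---|---|---|---|
| Negative | Negative | Excluded (item 2) | Not excluded | **No** |
| Positive, <200 | Negative | Excluded (item 3) | Not excluded | **No** |
| Positive, ≥200 | Negative | May participate (note) | Not excluded | Yes |
| Negative | Positive | Excluded (item 2) | Excluded | Yes |
| Positive, <200 | Positive | Excluded (items 3 and 4) | Excluded | Yes |
| Positive, ≥200 | Positive | Excluded (item 4) | Excluded | Yes |

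Conflicts: 2 of 6 profiles. All of them are DNA-negative, so they are 2 of the 3 DNA-negative profiles. [32] leaves 1 profile eligible; 8.2.8.3 leaves 3 not excluded; 3 − 1 = 2.

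Outside this group the texts agree. HBsAg-positive candidates are excluded by both, and candidates negative for both HBsAg and anti-HBc are excluded by neither.

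Cross-references for hepatitis B monitoring:

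- [32] note: cites 8.2.8.1 (hepatic safety monitoring), which is wrong.
- Schedule of Activities, footnote l: cites 8.2.8.1, also wrong.
- Appendix 2, footnote d: cites 8.2.8.3, which is correct.

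**The case against.** The strongest reply is that Section 5 controls enrolment. Any one exclusion criterion is enough to bar a candidate, Appendix 2 points to Section 5 for eligibility, Section 5 requires investigators to check all criteria, and Section 8 requires screening results to be reviewed against them. On this reading, not being excluded under 8.2.8.3 does not mean being cleared for entry: the candidate must still pass [32], and the HBsAb result that decides the matter is already in hand from Visit 1. Section 8.2.8.3 would then be an incomplete restatement under a testing-and-monitoring heading. The reply adds that anyone who did slip through would still have HBV DNA repeated at least every 3 months, since that section requires it whatever the HBsAb result, and that two of six serology cells says nothing about how many people are involved.

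Much of this stands. [32] is very probably meant to govern, the repeat DNA testing does limit the harm, and no participant count can be given. It does not remove the contradiction. No passage says which text prevails, and 8.2.8.3 states the opposite disposition outright. Appendix 2 offers limited protection: HBsAg, core antibody and HBV DNA carry the footnote pointing to the exclusion criteria, but HBsAb, the test that decides the disputed profiles, does not. Monitoring after entry also does not settle who may enter.

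**Conclusion.** The concern holds. Section 8.2.8.3 and exclusion [32] give opposite eligibility decisions for two of the three DNA-negative profiles among HBsAg-negative, anti-HBc-positive candidates, and two cross-references for hepatitis B monitoring point to the wrong section. This is an internal inconsistency in a safety-related entry rule and should be fixed. It does not touch the endpoints, analyses or sample size.

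The conclusion follows from the two texts alone and needs no outside figure. How many participants it would affect depends on the number screened and on the prevalence of core-antibody positivity with absent or low surface antibody. The protocol gives neither, so no estimate is made. The recommendation assumes that [32], the stricter rule, is the intended one, as Section 5.2 and Appendix 2 indicate.

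**What to change.** Let [32] govern, and amend three places:

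1. **Section 8.2.8.3.** Add HBsAb to the initial tests. Reword the DNA-negative branch so that the participant is not excluded only if HBsAb is at least 200 mIU/mL (see exclusion [32]) and is otherwise excluded. Keep the repeat HBV DNA testing for those who enter.
2. **Section 5.2, note to [32].** Change the reference from 8.2.8.1 to 8.2.8.3.
3. **Section 1.3, Schedule of Activities, footnote l.** Make the same change of reference.

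The cost is protocol-amendment wording. No new test or visit is needed, because HBsAb is already a Visit 1 eligibility test in Appendix 2, and no analysis changes.
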